6.12.5. Vital Signs

Vital signs will be measured at the time points indicated in the study procedures table ([Appendix 2](#)).

- Vital signs should be taken after the subject has been resting in the seated or supine position for at least 5 minutes and will include pulse rate, respiratory rate, systolic and diastolic blood pressure, and temperature.

6.12.6. Physical Examination

A physical examination should be performed at the time points indicated in the study procedures table [Appendix 2](#). Any changes from baseline will be recorded. Height will be measured at screening only. Subjects should be instructed to remove shoes prior to measurement of height.

At Screening, a complete physical examination will be performed. A complete physical examination should include source documentation of general appearance and the following body systems: head, neck, and thyroid; eyes, ears, nose, throat, mouth and tongue; chest (excluding breasts); respiratory; cardiovascular; lymph nodes; abdomen; skin, hair, nails; musculoskeletal; and neurological.

Symptom-driven physical examinations will be performed at all other visits based on reported signs and symptoms.

6.12.7. Other Safety Assessments

6.12.7.1. 12-lead Electrocardiogram

A resting 12-lead ECG will be performed at the time points indicated in the study procedures table ([Appendix 2](#)).

The ECG should be obtained after the subject has been resting in the supine position for at least 5 minutes and will include heart rate (HR), inter-beat (RR), QRS, uncorrected QT, morphology, and rhythm analysis. QT interval corrected for HR according to Fridericia (QTcF) will be derived during the statistical analysis. Electrocardiograms will be interpreted by the investigator (or qualified designee) for clinical significance and results will be entered into the eCRF.

6.13. Pharmacokinetics Assessments

Blood samples will be collected for plasma PK analysis of filgotinib and its active metabolite GS-829845, and GS-9876 post dose at Weeks 2, 4, and 20 (at least 30 minutes and up to 3 hours after dosing), anytime at Weeks 8 and 24, and within 2 hours prior to dosing at Weeks 16 and 32.

Urine PK analyses may be performed for filgotinib and its active metabolite GS-829845, and GS-9876, using the 24-hour urine collection at Week 16.

6.14. Biomarker Assessments

Urine samples will be collected for biomarker assessments at Screening, Day 1 (predose), Weeks 2, 16, 32, 52, ET, and at the Final FU.

Blood samples for biomarker assessments (whole blood TBNK biomarker, serum and plasma biomarkers, vfPBMC, and PAXgene RNA) will be collected at Screening, Day 1 (predose), Weeks 2, 16, 32, 52, ET, and at the Final FU.

CCI [REDACTED]

CCI [REDACTED]

[REDACTED]

7. ADVERSE EVENTS AND TOXICITY MANAGEMENT

7.1. Definitions of Adverse Events, Adverse Reactions, and Serious Adverse Events

7.1.1. Adverse Events

An adverse event (AE) is any untoward medical occurrence in a clinical study subject administered a medicinal product, which does not necessarily have a causal relationship with the treatment. An AE can therefore be any unfavorable and/or unintended sign, symptom, or disease temporally associated with the use of a medicinal product, whether or not considered related to the medicinal product. AEs may also include pre- or post-treatment complications that occur as a result of protocol specified procedures, lack of efficacy, overdose, drug abuse/misuse reports, or occupational exposure. Preexisting events that increase in severity or change in nature during or as a consequence of participation in the clinical study will also be considered AEs.

An AE does not include the following:

- Medical or surgical procedures such as surgery, endoscopy, tooth extraction, and transfusion. The condition that led to the procedure may be an adverse event and must be reported.
- Pre-existing diseases, conditions, or laboratory abnormalities present or detected before the screening visit that do not worsen
- Situations where an untoward medical occurrence has not occurred (eg, hospitalization for elective surgery, social and/or convenience admissions)
- Overdose without clinical sequelae (see Section 7.7)
- Any medical condition or clinically significant laboratory abnormality with an onset date before the consent form is signed and not related to a protocol-associated procedure is not an AE. It is considered to be pre-existing and should be documented on the medical history CRF.

7.1.2. Serious Adverse Events

A **serious adverse event** (SAE) is defined as an event that, at any dose, results in the following:

- Death
- Life-threatening (Note: The term “life-threatening” in the definition of “serious” refers to an event in which the subject was at risk of death at the time of the event; it does not refer to an event that hypothetically might have caused death if it were more severe.)
- In-patient hospitalization or prolongation of existing hospitalization

- Persistent or significant disability/incapacity
- A congenital anomaly/birth defect
- A medically important event or reaction: such events may not be immediately life-threatening or result in death or hospitalization but may jeopardize the subject or may require intervention to prevent one of the other outcomes constituting SAEs. Medical and scientific judgment must be exercised to determine whether such an event is a reportable under expedited reporting rules. Examples of medically important events include intensive treatment in an emergency room or at home for allergic bronchospasm; blood dyscrasias or convulsions that do not result in hospitalization; and development of drug dependency or drug abuse. For the avoidance of doubt, infections resulting from contaminated medicinal product will be considered a medically important event and subject to expedited reporting requirements.

7.2. Assessment of Adverse Events and Serious Adverse Events

The investigator or qualified subinvestigator is responsible for assessing AEs and SAEs for causality and severity, and for final review and confirmation of accuracy of event information and assessments.

7.2.1. Assessment of Causality for Study Drugs and Procedures

The investigator or qualified subinvestigator is responsible for assessing the relationship to IMP treatment using clinical judgment and the following considerations:

- **No:** Evidence exists that the adverse event has an etiology other than the IMP. For SAEs, an alternative causality must be provided (eg, pre-existing condition, underlying disease, intercurrent illness, or concomitant medication).
- **Yes:** There is reasonable possibility that the event may have been caused by the investigational medicinal product.

It should be emphasized that ineffective treatment should not be considered as causally related in the context of adverse event reporting.

The relationship to study procedures (eg, invasive procedures such as venipuncture) should be assessed using the following considerations:

- **No:** Evidence exists that the adverse event has an etiology other than the study procedure.
- **Yes:** The adverse event occurred as a result of protocol procedures, (eg., venipuncture)

7.2.2. Assessment of Severity

The severity of AEs will be graded using the modified CTCAE, version 4.03. For each episode, the highest grade attained should be reported. For AEs associated with laboratory abnormalities, the event should be graded on the basis of the clinical severity in the context of the underlying conditions; this may or may not be in agreement with the grading of the laboratory abnormality.

If a CTCAE criterion does not exist, the investigator should use the grade or adjectives: Grade 1 (mild), Grade 2 (moderate), Grade 3 (severe), Grade 4 (life-threatening) or Grade 5 (fatal) to describe the maximum intensity of the adverse event. For purposes of consistency with the CTCAE, these intensity grades are defined in [Table 7-1](#) and [Appendix 4](#).

Table 7-1. Grading of Adverse Event Severity

Grade	Adjective	Description
Grade 1	Mild	Asymptomatic or mild symptoms; clinical or diagnostic observations only; intervention not indicated
Grade 2	Moderate	Local or noninvasive intervention indicated; limiting age-appropriate instrumental ADL
Grade 3	Severe	Severe or medically significant but not immediately life-threatening; hospitalization or prolongation of hospitalization indicated; disabling; limiting self-care ADL
Grade 4	Life-threatening	Urgent intervention indicated
Grade 5	Death	Death related AE

* Activities of Daily Living (ADL) Instrumental ADL refer to opening preparing meals, shopping for groceries or clothes, using the telephone, managing money, etc.

** Self-care ADL refer to bathing, dressing and undressing, feeding self, using the toilet, taking medications, and not bedridden

7.3. Investigator Requirements and Instructions for Reporting Adverse Events and Serious Adverse Events to Gilead

Requirements for collection prior to study drug initiation:

After informed consent, but prior to initiation of study medication, the following types of events should be reported on the case report form (CRF/eCRF): all SAEs and adverse events related to protocol-mandated procedures.

Adverse Events

Following initiation of study medication, all AEs, regardless of cause or relationship, until 30-days after last administration of study drug(s) must be reported to the CRF/eCRF database as instructed.

All AEs should be followed up until resolution or until the adverse event is stable, if possible. Gilead Sciences may request that certain AEs be followed beyond the protocol defined follow up period.

Serious Adverse Events

All SAEs, regardless of cause or relationship, that occurs after the subject first consents to participate in the study (ie, signing the informed consent) and throughout the duration of the study, including the protocol-required post treatment follow-up period, must be reported to the CRF/eCRF database and Gilead Pharmacovigilance and Epidemiology (PVE) as instructed. This also includes any SAEs resulting from protocol-associated procedures performed after informed consent is signed.

Any SAEs and deaths that occur after the post treatment follow-up visit but within 30-days of the last dose of study drug(s), regardless of causality, should also be reported.

Investigators are not obligated to actively seek SAEs after the protocol defined follow up period. However, if the investigator learns of any SAEs that occur after study participation has concluded and the event is deemed relevant to the use of study drug(s), he/she should promptly document and report the event to Gilead PVE.

- All AEs and SAEs will be recorded in the CRF/eCRF database within the timelines outlined in the CRF/eCRF completion guideline.

Electronic Serious Adverse Event (eSAE) Reporting Process

- Site personnel record all SAE data in the eCRF database and from there transmit the SAE information to Gilead PVE within 24 hours of the investigator's knowledge of the event. Detailed instructions can be found in the eCRF completion guidelines.
- If for any reason it is not possible to record the SAE information electronically, ie, the eCRF database is not functioning, record the SAE on the paper serious adverse event reporting form and submit within 24 hours to:

Gilead PVE:

Fax:

PPD

E-mail:

PPD

- As soon as it is possible to do so, any SAE reported via paper must be transcribed into the eCRF Database according to instructions in the eCRF completion guidelines.
- If an SAE has been reported via a paper form because the eCRF database has been locked, no further action is necessary.
- For fatal or life-threatening events, copies of hospital case reports, autopsy reports, and other documents are also to be submitted by e-mail or fax when requested and applicable. Transmission of such documents should occur without personal subject identification, maintaining the traceability of a document to the subject identifiers.

- Additional information may be requested to ensure the timely completion of accurate safety reports.
- Any medications necessary for treatment of the SAE must be recorded onto the concomitant medication section of the subject's CRF/eCRF and the event description section of the SAE form.

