8.6.2. Adverse Events

Clinical and laboratory AEs will be coded using the Medical Dictionary for Regulatory Activities (MedDRA). System Organ Class (SOC), High-Level Group Term (HLGT), High-Level Term (HLT), Preferred Term (PT), and Lower-Level Term (LLT) will be attached to the clinical database.

Treatment-emergent adverse events (TEAEs) are defined as one or both of the following:

- Any AEs with an onset date on or after the study drug start date and no later than 30 days after permanent discontinuation of study drug.
- Any AEs leading to premature discontinuation of study drug.

Summaries (number and percentage of subjects) of treatment-emergent adverse events (by SOC, and PT) will be provided. TEAEs will also be summarized by relationship to study drug and severity.

All observed AEs will be presented in by-subject listings.

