7.1.5. Treatment-Emergent Adverse Events

7.1.5.1. Definition of Treatment-Emergent Adverse Events

Treatment-emergent adverse events (TEAEs) are defined as 1 or both of the following:

- Any AEs with an onset date on or after the study drug start date and no later than 30 days after permanent discontinuation of study drug
- Any AEs leading to premature discontinuation of study drug.

TEAEs of treatment period Up to Week 16 are defined as 1 or both of the following:

- Any AEs with an onset date on or after first dosing date of a treatment period, prior to the first dose of treatment at Week 16. For subjects who did not continue treatment past Week 16, any AEs with an onset date on or after the study drug start date and no later than 30 days after permanent discontinuation of study drug
- Any AEs leading to premature discontinuation of study drug prior to Week 16 dosing

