7.1.6. Summaries of Adverse Events and Deaths

Treatment-emergent AEs will be summarized based on the Safety Analysis Set. The tables will be presented by treatment period.

A brief, high-level summary of the number and percentage of subjects who experienced at least 1 TEAE in the categories described below will be provided by treatment group. All deaths observed in the study will also be included in this summary.

The number and percentage of subjects who experienced at least 1 TEAE will be provided and summarized by SOC, PT, severity and treatment group for the following:

- All TEAEs
- All TE treatment-related AEs
- All TE SAEs
- TEAEs of interest

For the AE categories described below, summaries will be provided by SOC, PT, and treatment group:

- TEAEs of Grade 3 or higher (by maximum severity)
- TE treatment-related AEs of Grade 3 or higher (by maximum severity)
- All TE treatment-related SAEs
- All TEAEs leading to premature discontinuation of study drug
- All TEAEs leading to premature discontinuation of study

Multiple events will be counted only once per subject in each summary. Adverse events will be summarized and listed first in alphabetic order of SOC and then by PT in descending order of total frequency within each SOC. For summaries by severity grade, the most severe grade will be used for those AEs that occurred more than once in an individual subject during the study.

In addition, data listings will be provided for the following:

- All AEs, indicating whether the event is treatment emergent
- SAEs
- Deaths
- AEs leading to premature discontinuation of study drug or study
- TEAEs of interest

Adverse events of interest will be identified by the use of either Standardized MedDRA queries or MedDRA search terms.

The following adverse events of interest will be presented:

- All infections (defined as all PTs within the Infections and Infestations SOC)
- Serious infections (defined as all PTs within the Infections and Infestations SOC that are SAEs)
- Herpes Zoster infection
- Opportunistic infections
- Active tuberculosis
- Hepatitis B and C

- Serious Major Adverse Cardiovascular Events (MACE)

Unstable angina

Cardiac failure

Stroke

Transient ischemic attack

Percutaneous coronary intervention

Myocardial Infarction

- Gastrointestinal perforation
- Venous thrombotic events and pulmonary embolism
- Malignancy including non-melanoma skin cancer
- Transaminases increased

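### An adverse event that worsens after the Week 16 drug change is tabulated at its later, higher grade in the pre-switch period, under the first drug

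*Protocol*

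**What the plan says.** Four rules meet here.

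- **Grade.** Protocol 7.2.2 asks for one severity value per episode: "For each episode, the highest grade attained should be reported". It does not say when the grade must have been reached.
- **Overall TEAE.** Protocol 8.6.2 and SAP 7.1.5.1 define a TEAE by onset ("Any AEs with an onset date on or after the study drug start date and no later than 30 days after permanent discontinuation") or by having led to premature discontinuation of study drug. This definition has no periods.
- **Period TEAE.** SAP 7.1.5.1 adds a definition for the period up to Week 16, with onset "on or after first dosing date of a treatment period, prior to the first dose of treatment at Week 16". A second limb covers AEs that led to discontinuation before Week 16 dosing. No definition follows for Weeks 16 to 32 or for Week 32 to the end of the study.
- **Tables.** SAP 7.1.6 says of the TEAE summaries: "The tables will be presented by treatment period". They include breakdowns by severity, by Grade 3 or higher and by seriousness.

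Under Protocol 3.3 and SAP 1.2, a subject whose urinary protein falls by less than 35% at Week 16 is switched, blinded, to the other drug. A further change is possible at Week 32.

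**The concern.** An AE that is still going on at the Week 16 visit is one episode, and its recorded grade may have been reached after the drug changed. The period rule looks at onset and ignores when the grade was reached. The first-period severity table can therefore show a grade that the subject never had while on the first drug.

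The period up to Week 16 is the only stretch in which the two drugs can be compared as randomized, before any switching. Safety and tolerability of each drug is a secondary objective, and the TEAE tables are kept in the abbreviated report. Protocol section 8 opens by saying that safety data collected up to Week 16 will be summarized by treatment group. A grade first reached in a later week does not fit that description.

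**Working it through.** The plan states no figure on this point, so there is none to reproduce. The check applies the written rules to one example and then sizes a single event.

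**Inputs**
- Grade of an episode: the maximum over the whole episode (Protocol 7.2.2).
- First-period rule: first dose ≤ onset < first Week 16 dose (SAP 7.1.5.1).
- Week 16 target: Day 113 (SAP Table 3-1).
- Example, assumed: Grade 1 onset on Day 100, drug change on Day 113, Grade 3 on Day 120, one continuing episode.
- Planned arm size 16 (Protocol 8.9); 9 subjects randomized (SAP 1.3). A split of 4 and 5 is an assumption.

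**Step 1: the rules as written**
- Period: 1 ≤ 100 < 113 is true, so the event is a TEAE of the period up to Week 16.
- Grade: max(1, 3) = 3.
- Result: a Grade 3 TEAE under the first drug, although the highest grade reached before Day 113 was 1.

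**Step 2: the later period**
- The SAP has no TEAE definition here, so no written rule counts the worsening.
- If the onset rule were carried forward, 100 ≥ 113 is false and the event would not be counted. That is a projection of the rule and is not stated in the text.

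**Step 3: does another rule correct this?**
- Protocol 7.1.1 treats worsening as an AE for "Preexisting events that increase in severity or change in nature during or as a consequence of participation in the clinical study". Nothing equivalent is written for an on-study AE that worsens after a change of drug.
- SAP 7.1.6 says: "For summaries by severity grade, the most severe grade will be used for those AEs that occurred more than once in an individual subject". This concerns repeated events and takes the higher grade. It does not limit the grade to a period.
- SAP 7.1.3 collects relatedness separately for each drug, but an AE related to either one counts as related to study treatment in the summaries.
- SAP 7.2.2.1 defines treatment-emergent laboratory abnormalities by a rise in grade from baseline. AE records have no such rule.
- SAP section 2 plans only a final analysis after all subjects finish, so grades reached after Week 16 will already be in the records when the first-period table is made.

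**Step 4: grade taken by period**
- Day 100, Grade 1: first period, Grade 1.
- Day 120, Grade 3: later period, Grade 3.

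**Step 5: size of one event in the first-period Grade 3 or higher row**, for a subject with no other event in that row
- Planned size: 1/16 = 6.25 percentage points.
- Arm of 5: 1/5 = 20 points.
- Arm of 4: 1/4 = 25 points.

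No figure can be given for a later-period column. Its denominator is the number of subjects on each drug after the switch, which the documents do not give.

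**The case against.** The strongest reply is that a single record per episode is an inference. Protocol 7.2.2 does not define an episode, and Protocol 7.3 leaves recording details to the eCRF completion guidelines, which may tell sites to open a new record when an AE worsens. If they do, the problem disappears, and citing that rule in the SAP would settle it. This stands as a condition on the point.

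Three stronger readings are tempting, and the documents do not support them.

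- **The second drug's column loses the event by an equal amount.** No later-period TEAE rule exists, so no written rule excludes the event either. SAP 3.2 moves a subject out of the randomized group only if treatment differed for the entire treatment period. Read literally, a subject who switches may stay under the first drug throughout, and there may be no second-drug column.
- **The worsening belongs to the second drug.** The documents use a 30-day window after the last dose and describe no washout. Day 120 is 7 days after the switch; even Week 20 (Day 141) is only 28 days after Day 113. Attribution to either drug is uncertain in that window.
- **Every AE ongoing at Week 16 is affected.** A subject who stays on the same drug may have a grade placed in an earlier period than it occurred, but not under the wrong drug.

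On materiality, the report is abbreviated, all AEs remain in by-subject listings, and no such event is known to have occurred. All of this is fair and limits the point to the summary tables. It does not make the first-period grade correct.

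**Conclusion.** The point holds for the first-period tables. Following Protocol 7.2.2 with SAP 7.1.5.1 and 7.1.6, an AE with onset before the first Week 16 dose that worsens after a drug change is tabulated at the later grade under the first drug. The condition is that the eCRF completion guidelines do not already require a new record on worsening.

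Each such event overstates the first drug's Grade 3 or higher count by one subject, with the size shown in the last step of the working. The 20 to 25 point range rests on the assumed split of the 9 subjects. The number of such events cannot be known from the documents. A reader might infer a mirror-image loss on the second drug; the documents establish only that the SAP has no rule for counting a worsening in the later periods. The same question arises for a drug change at Week 32.

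**What to change.** Limit the rule to subjects who actually change drug at Week 16 or Week 32.

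- **Earlier period.** In that period's tables, use only the highest grade and the seriousness reached before the first dose of the new drug.
- **Later period.** If an ongoing AE rises in grade, becomes serious or leads to discontinuation after that dose, record the date of worsening and count it as a TEAE of the later period.
- **Footnote.** Mark such events as ongoing at the switch, and state that worsening within 30 days of the first drug's last dose cannot be assigned cleanly to either drug.
- **SAP 7.1.5.1.** Add TEAE definitions for Weeks 16 to 32 and for Week 32 to the end of the study, based on onset or worsening.
- **Recording.** Put the matching instruction in the eCRF completion guidelines, or cite it in the SAP if it is already there.

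The first-dose dates for Day 1, Week 16 and Week 32 are already on the CRF (SAP 3.8.1), and only 9 subjects need review, which can be done before the blind is broken. The costs are retrospective site queries for a few AEs, reconciliation of any changed serious AE records with the safety database (SAP 7.1.4), and the chance that one continuing event appears in two periods. The change affects recording and tabulation only.
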